1.1 Study Objective

Developing interventions against age-associated cognitive decline is especially important, given the increase of aging populations around the world. Implementing combined cognitive training and transcranial direct current stimulation (tDCS) interventions has been beneficial in the past, supporting training effects and enabling transfer to other cognitive domains (Jones et al., 2015; Perceval et al., 2016; Berryhill, 2017; Antonenko et al., 2018; Antonenko et al., 2022). However, access to clinical centers offering multisession tDCS-accompanied cognitive training is limited. In order to increase accessibility, we conducted a clinical trial regarding the home-based and remote supervised application of tDCS in healthy older adults. We aim to provide evidence for the feasibility and the effects of a multisession home-based cognitive training in combination with tDCS on cognitive functions in healthy older adults (see Thams et al., 2022 for study protocol). The analyses described in this statistical analysis plan (SAP) will demonstrate the feasibility and efficacy of a two-week cognitive training intervention with concurrent tDCS in healthy older adults.

This SAP was prepared in accordance with the *Guidelines for the Content of Statistical Analysis Plans in Clinical Trials* (Gamble et al., 2017).

1.2 Primary hypothesis

The primary hypothesis of the project is that the self-application of tDCS combined with cognitive training by participants themselves in an ecologically valid environment (i.e., at participant's home) is feasible. Feasibility will operationalized by two-thirds of successfully performed interventional sessions per participant for at least 60 % of all participants. A session is considered successful when it is registered as fully completed in the cloud and the participant has not initiated contact concerning a problem or rescheduling.

1.3 Secondary hypotheses

Secondary hypotheses state that the combination of cognitive training and tDCS is superior compared to cognitive training alone with regard to cognitive training tasks, transfer tasks, at all follow up measures as defined by the secondary outcomes in healthy older adults.

1.4 Study Design

The TrainStim-Home trial is a randomized, double-blind, placebo-controlled monocenter study. The experimental group receives a six-session cognitive training intervention over two weeks, accompanied by tDCS over the left dorsolateral prefrontal cortex (DLPFC). The intervention of the control group consists of the same six-session cognitive training combined with sham stimulation.

Random allocation to experimental and control groups, respectively, will be performed with a 1:1 ratio. Stratified block randomization will be used. Strata will be chosen according to age (60-70 and 71-80 years) and initial performance in the letter updating task (≤ 5 , $\geq 5/25$ correctly recalled lists). After successful completion of telephone screening and baseline assessment (defined as meeting all eligibility criteria) and giving written informed consent, participants will be divided into four groups according to the age and performance strata. For the randomization we will use the blockrand package

in R¹.

1.5 Sample Size Calculation

As the primary goal of this study will be to assess feasibility, and as it is recommended to employ results of feasibility trials for sample size calculation of a planned subsequent trial (Hagen et al., 2011), we chose a sample size of N = 30 (Rahbek et al., 2017). To infer feasibility, the lower bound of the 95 % confidence interval of the proportion of participants who fulfilled the feasibility criterion needs to be at 60 %. Thus, 76 %, i.e., n = 23 participants will have to meet the feasibility criterion.

With 15 participants per stimulation group (anodal vs. sham stimulation), we will be able to scope the general feasibility of this home-based intervention and explore descriptively the benefit of anodal tDCS over sham with regard to performance after the training on the trained and untrained working memory tasks to obtain estimates of effect sizes for power calculations of future randomized controlled trials (Elmasry et al., 2015; Antonenko et al., 2018). Using an independent t-test with a two-sided significance level of 0.05 and a power of 80 % we will be able to demonstrate an effect of Cohen's d = 1.06 or higher on behavioral performance. Since this effect size is high and might be unrealistic, we use the secondary analyses on efficacy measures solely exploratory to inform future trials.

2 Analysis sets

2.1 Definitions

The **full analysis set** will consist of all participants who received at least one day of intervention. In case participants withdraw informed consent after baseline assessment, they will be considered as screening failures and therefore will not be included in the full analysis set. The **per protocol analysis set** comprises all subjects who successfully completed two-thirds of the home-based sessions (thus fulfilling the criterion for feasibility). Safety measures will be assessed during tDCS intervention and all participants who received at least one day of intervention will be included according to their actual treatment in **the safety analysis set**.

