4.2 Primary Outcome

Primary outcome measure will be the feasibility of home-based, remotely-controlled and independently self-applied tDCS combined with cognitive training. Feasibility will inferred if 60% of the participants will have successfully performed two thirds (n= 4) of the planned sessions. A session is defined as successful when it is registered as fully completed in the cloud and the participant has not initiated contact concerning a problem or rescheduling.

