6.2 Secondary analyses

Secondary feasibility outcome, as measured by questionnaire (percentage of participants with high satisfaction tDCS and training equipment), will be analyzed similarly to the primary outcome. The point estimate and the 95%CI of the feasibility criterion (according to the Agresti & Coull formula) will be presented.

Data distributions of the questionnaire items will be visually assessed for normality using q-q plots.

Data on behavioral tasks from all participants (included at randomization and completed post-assessment) will be analyzed using linear mixed models. (See details below)

Additionally, a subgroup analysis will include only those participants who successfully completed two-thirds of the home-based sessions (thus fulfilling the criterion for feasibility; per protocol analyses).

Training task effects

Using linear mixed models (random intercept models accounting for clustering of measures within individuals), the performance of the letter updating task over the study period including all measures after start of intervention V2-V9 will be used as dependent variable, stimulation group (tDCS, sham) as factor, and letter updating performance at pre-assessment as well as age and sex as covariates. The time point of measure will also be included as variable and will be modelled as categorical variable or as continuous variable that reflects the changes over time. Additionally, an interaction term for group X time point will be included to model differential changes over time in both groups. The letter updating task score at post assessment will be evaluated between treatment groups based on this regression model via marginal means to examine immediate training effects. The letter updating task

score at fu assessment will be evaluated between treatment groups based on this regression model via marginal means to examine sustained training effects.

Transfer task effects

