6.4 Planned subgroup analyses

We will conduct subgroup analyses regarding participant's cognitive reserve, operationalized by their education years and their commitment to the intervention, operationalized by the number of successful conducted training sessions. Subgroups will be achieved through median splits.

All subgroup analyses will be done within an exploratory framework, using descriptive analyses.

6.5 Example table for the description of baseline characteristics Table 2. Baseline characteristics of the study sample.

	All	TDCS group	Sham group
	n =	n =	n =
Age (years)			
Gender (n, % female)			
Education (years)			
GDS			
Semantic fluency			
BNT (max. 15)			
MMSE (max. 30)			
Word list learning			
Total (max. 30)			
Trial 1 (max. 10)			
Trial 2 (max. 10)			
Trial 3 (max. 10)			
Word list retrieval (max. 10)			
Word list intrusions			
Figure copying (max. 11)			
Figure retrieval (max. 11)			
Phonematic fluency			
Trail-making test			
Part A (sec)			
Part B (sec)			
Digit-span			
Forward			
Backward			
Data are shown as the mean (SD) or n(9	%). GDS, Geriatric I	Depression Scale. BNT, Bos	ton Naming Test. MMSE, Mini

Mental Status Examination. RT, reaction time.

7. References

- Antal A et al. (2017) Low intensity transcranial electric stimulation: Safety, ethical, legal regulatory and application guidelines. Clin Neurophysiol 128:1774-1809.
- Berryhill ME (2017) Longitudinal tDCS: Consistency across Working Memory Training Studies. AIMS Neuroscience 4:71-86.

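### The per-protocol set reuses the contact-free feasibility criterion, so it can exclude participants who completed all six sessions and does not reflect treatment received

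*SAP*

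**What the plan says.** SAP 1.4 sets the course of treatment: "The experimental group receives a six-session cognitive training intervention over two weeks", and the control group has the same schedule with sham. SAP 4.2 (and 1.2 in the same terms) makes a session successful when it is "registered as fully completed in the cloud and the participant has not initiated contact concerning a problem or rescheduling". A participant meets the feasibility criterion after having "successfully performed two thirds (n= 4) of the planned sessions".

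SAP 2.1 carries this count into the per-protocol set, which "comprises all subjects who successfully completed two-thirds of the home-based sessions", and equates membership with meeting the feasibility criterion. SAP 6.2 then applies it to the behavioural tasks: "a subgroup analysis will include only those participants who successfully completed two-thirds of the home-based sessions", labelled there as per protocol. SAP 6.4 uses the count once more, for a median split on commitment, "operationalized by the number of successful conducted training sessions".

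The main efficacy analysis uses the full analysis set (2.2), and all secondary analyses are exploratory (1.5, 6.2). The SAP defines no analysis set by sessions completed alone.

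**The concern.** The no-contact condition fits the primary question, which is whether participants can run the intervention at home by themselves. It is not a measure of whether training and stimulation were delivered. A participant may call about a problem or a change of date and still complete the session in full, yet that session no longer counts.

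Readers generally take a per-protocol efficacy result to describe people who were adequately treated. This one describes people who seldom asked for help, and asking for help is behaviour after randomisation. If contact is more frequent in one arm, for instance because sensations of the kind listed in 4.4 prompt calls, and if those who call also perform differently, the per-protocol contrast mixes selection with treatment effect. According to 1.5, the efficacy estimates are meant to inform power calculations for later trials, so a misread per-protocol estimate would have a use beyond this report.

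In 6.4, someone who met difficulties, called, and finished all six sessions scores low on commitment.

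**Working it through.** **Inputs from the SAP.** Six sessions (1.4); threshold of four successful sessions (4.2); N = 30, 15 per group (1.5); feasibility counts of 23 of 30 (1.5) and 18 of 30 (6.1). The SAP gives no contact rate, so every rate below is an assumption.

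**The plan's own figures.** Threshold: 2/3 × 6 = 4, as stated. Detectable effect: a two-sample t-test with 15 per group, two-sided 0.05 and 80% power gives d = 1.0598, which matches the stated 1.06.

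**Who is in the set.** For a participant with all six sessions completed and k of them with contact, successful sessions = 6 − k.
- k = 0, 1, 2 gives 6, 5, 4: included.
- k = 3 gives 3, and larger k gives fewer: excluded.
- Counting cloud completion alone, the total is 6 for any k: included.

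**Chance of exclusion despite six completed sessions.** With an independent contact probability q per session,
P(k ≥ 3) = 1 − [(1−q)^6 + 6q(1−q)^5 + 15q²(1−q)^4].
- q = 0.10: 1 − (0.5314 + 0.3543 + 0.0984) = 0.0159; × 30 = 0.5 participants.
- q = 0.20: 1 − (0.2621 + 0.3932 + 0.2458) = 0.0989; × 30 = 3.0 participants.

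The multiplication by 30 assumes that all 30 complete six sessions.

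**Higher rates against the plan's own target.** Set members are by definition the participants who meet the feasibility criterion.
- q = 0.25: 0.169 × 30 = 5.1 excluded, 24.9 expected to remain, still above 23.
- q = 0.30: 0.256 × 30 = 7.7 excluded, 22.3 remain, below 23 but above 18.
- q = 0.40: 0.456 × 30 = 13.7 excluded, 16.3 remain, below both.

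So from about 30% upward the trial would be expected to miss the 23-of-30 target, and that would be its main result. If 23 is reached, at most 30 − 23 = 7 participants are outside the set for any reason.

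**Precision.** With 13 per group, close to the loss at q = 0.20, the detectable d rises from 1.06 to 1.15.

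**Can the contrast be biased?** This was simulated with no true effect, 200,000 participants per arm, a standard normal performance score, and log-odds of contact falling with performance by an assumed slope per SD.
- Equal rates in both arms (0.20 v 0.20), any slope: bias about 0.
- Unequal rates, slope 0: bias about 0.
- Base rates 0.30 v 0.20, slope 0.5 to 1: 0.12 to 0.16 SD.
- Base rates 0.30 v 0.10, slope 0.5 to 1: 0.22 to 0.32 SD.

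The bias favours the arm with more contact, because its poorer performers are removed. The simulation does not adjust for pre-assessment performance, which the models in 6.2 do. The adjusted bias would be smaller to the extent that pre-assessment performance explains who calls.

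**The case against.** The strongest reply is that the SAP hides nothing. In 2.1 and 6.2 the set is tied in the same sentence to the feasibility criterion, and the hypothesis in 1.2 concerns self-application. The effect among independent self-users is a coherent subgroup. This stands. A reader might infer that the SAP intends a dose-based comparison and fails to deliver it, but the SAP nowhere describes the set in those terms. What remains is that the per-protocol label invites that reading and no other set measures treatment received.

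A reader might also infer that the efficacy comparison is distorted. The documents do not support that. Bias needs contact to differ by arm and to be related to performance. The trial is double-blind and sham-controlled, and no figures are given for either condition. Nor are participants lost to the trial, since those excluded here stay in the full analysis set.

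Third, a session with a call is not necessarily equivalent to one without. A rescheduled session departs from the planned timing, and the SAP does not say that a complete cloud record rules out a compromised session. That is fair, and it means that some such exclusions could be defended. It does not justify excluding every session with participant-initiated contact of this kind from a set read as treatment received.

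Finally, one might want to replace the count in 6.4 by completed sessions as well. That does not follow: if most participants complete all six, the count is at its ceiling and a median split may not separate anyone.

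**Conclusion.** The point holds in limited form. It follows from 2.1, 4.2 and 6.2 read together, without any assumption, that a participant with six completed sessions and contact about three or more is outside the per-protocol set. The per-protocol efficacy analysis therefore does not reflect treatment received.

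The likely size is small: about 0.5 to 3 of 30, assuming contact rates of 10% to 20% per session, independence between sessions, and six completed sessions for everyone. Bias between arms is possible but not shown, and its simulated size rests wholly on assumed rates and slopes.

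The consequence is confined to an additional exploratory analysis and the commitment split. This is an inexpensive improvement to the SAP and does not threaten the trial's conclusions.

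**What to change.** 1. Keep the contact-free definition of a successful session for the primary feasibility outcome (1.2, 4.2, 6.1).
2. In 2.1 and 6.2, define the per-protocol set as participants with at least 4 of 6 sessions registered as fully completed in the cloud, regardless of contact.
3. If the present subgroup is wanted, report it separately under the name *feasibility responders*.
4. In 6.4, keep the successful-session count but describe it as independent completion rather than commitment. Do not substitute a median split on completed sessions.

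The cost is wording only, because cloud completion is already recorded (4.2 and Table 1). The small downside is that two counts must be reported and the per-protocol set no longer equals the feasibility responders.

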2.2 Application

The efficacy analysis regarding the effect of tDCS-accompanied training on working memory performance will be done using the full analysis set. For the safety analysis, analysis will be done in the safety analysis set, which is the same as the full analysis set.

3 Trial centres

Participants will be recruited in one centre: Greifswald.

3.1 Recruitment

Participants will be recruited through advertisements in the local newspapers and distribution of flyers in local senior citizen clubs. Telephone screenings will be conducted with all potential participants and

¹ http://www.R-project.org, http://www.rstudio.com, https://CRAN.R-project.org/package=blockrand

study information will be provided. Eligible candidates will be invited for baseline assessment. Following baseline assessment (V0) participants will be included if neuropsychological testing is unobtrusive.

Information on recruitment flow can be found in the CONSORT flow diagram (Figure 1).

[figure not shown]

Figure 1. TrainStim-Cog study flowchart. tDCS, transcranial direct current stimulation. Obtained from TrainStim-Home study protocol (Thams et al., 2022).

4 Analysis variables

Table 1. TrainStim-Home outcome measures.

Adapted from TrainStim-Home study protocol (Thams et al., 2022)

			Baseline	Pre	T1-T6	Post	FU
					(2 weeks)	(3 days)	(1 month)
			~3h	~1,5h	~1h	~1,5h	~1,5h
Time point	Measurement	Mode	V0	V1	V2-V7	V8	V9
Enrollment							
Eligibility screening		Paper	х				
Informed consent		Paper	х				
Neuropsychological Screening	Demographic data	Paper	х				
	Geriatric depression scale(Brink et al., 2013)	Paper	х				
	Oldfield handedness inventory(Oldfield, 1971)	Paper	х				
	CERAD Plus(Morris et al., 1989)	Paper	х				
	Digit Span(Lezak et al., 2004)	Paper	х				
Intervention					\leftrightarrow		
Training task	Letter	Tablet	х	Х	х	Х	Х
	updating(Dahlin et al., 2008; Passow et al., 2017)	computer					
Brain stimulation	tDCS (anodal vs. sham)	Device			х		
Questionnaires	Self-reported	Paper		Х	х	Х	х
	well-being						
	questionnaire						
	PANAS(Watson et al., 1988)	Paper			x		
	Adverse events questionnaire(Antal et al., 2017)*				х		

"Cognitive Training Combined With Transcranial Direct Current Stimulation in Older Adults in a Home-based Context" Acronym: TrainStim-Home

Additional assessment	ts					
Untrained task	n-back(Lezak et al., 2012)	Computer	х		х	Х
Feasibility	Sessions completed	Cloud		Х	Х	
	(primary outcome)	system				
	Feasibility questionnaire	Paper			Х	

Abbreviations: T1-T6, training 1-6; FU, follow-up-assessment; V0-V9, visits 0-9; CERAD Plus, The Consortium to Establish a Registry for Alzheimer's Disease, neuropsychological test battery, German version, extended to CERAD Plus with the Trail Making Test A + B and Phonematic Fluency (S-Words); tDCS, transcranial direct current stimulation; PANAS, positive and negative affect schedule. All measures were acquired on site or at the respective participants home, except for screening which was done via telephone. *assessed only at the end of each training week (V4 and V7).

4.2 Primary Outcome

Primary outcome measure will be the feasibility of home-based, remotely-controlled and independently self-applied tDCS combined with cognitive training. Feasibility will inferred if 60% of the participants will have successfully performed two thirds (n= 4) of the planned sessions. A session is defined as successful when it is registered as fully completed in the cloud and the participant has not initiated contact concerning a problem or rescheduling.

4.3 Secondary Outcomes

Feasibility

- feasibility will be inferred additionally, if the questionnaire item assessing overall satisfaction with tDCS and training equipment is rated by a participant with 'agree' or 'strongly agree' in 60 % of all participants

At post- and follow-up assessments (V8, V9 the following secondary outcome measures will be analyzed:

Training task

- working memory performance in the trained task (operationalized by number of correctly recalled lists at each session)

Transfer task

- Performance on numeric n-back task (% correct, d-prime)

4.4 Safety Outcomes

Safety parameters are assessed via self-report questionnaire every third day of training (V4, V7). The questionnaire was adapted from Antal et al. (2017) and includes intensity ratings with regard to itching, pain, burning, warmth/heat, metallic/iron taste, fatigue/decreased alertness and other sensations.

5 Handling of missing values

Primary outcome of this trial is the feasibility of the intervention. For the primary outcome no missing value imputation will be done, since missing information is related to non-adherence of the participants. Secondary efficacy outcome analyses will be done using complete data without any imputation, due to the small sample size and the exploratory framework of the study.

6 Statistical analyses

For all analyses (including the analysis of the primary outcome) appropriate descriptive statistics (absolute score, mean, standard deviation, median, interquartile range, absolute and relative frequencies) depending on the scale and distribution of the outcome variable will be presented.

Statistical analyses will be divided to analyze

- 1. feasibility
- 2. training effects on letter updating task (at post and 1 month follow-up)
- 3. transfer effects on n-back task (at post and 1 month follow-up)

Training and transfer measures will be corrected for performance at pre-assessment.

6.1 Primary analysis

Feasibility data (primary outcome) will be analyzed using descriptive statistics. Feasibility will be inferred when 60 % of the participants (n =18) complete at least two-thirds (n=4) of the home-based sessions successfully. The point estimate of the primary feasibility criterion and the corresponding 95% CI will be calculated and presented. The 95%CI will be calculated using the formula of Agresti & Coull (Agresti A., Coull B.A. Approximate is better than 'exact' for interval estimation of binomial proportions. Am. Stat. 1998;52:119–126. doi: 10.2307/2685469).

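### The SAP gives two incompatible rules for declaring feasibility (18 of 30 versus 23 of 30), and 23 of 30 fails the Agresti-Coull interval that the SAP names

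*SAP*

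**What the plan says.** Section 1.5 sets the sample size ("we chose a sample size of N = 30") and states a condition for inferring feasibility: "the lower bound of the 95 % confidence interval of the proportion of participants who fulfilled the feasibility criterion needs to be at 60" percent. It then gives the count: "Thus, 76 %, i.e., n = 23 participants will have to meet the feasibility criterion".

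Section 4.2 defines the primary outcome by the observed proportion alone: "Feasibility will inferred if 60% of the participants will have successfully performed two thirds (n= 4) of the planned sessions". Section 6.1 repeats that rule with a count: "Feasibility will be inferred when 60 % of the participants (n =18) complete at least two-thirds (n=4) of the home-based sessions successfully". In 6.1 the confidence interval is to be calculated and reported, with no threshold attached. Its method is fixed: "The 95%CI will be calculated using the formula of Agresti & Coull".

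Section 1.2 names at least 60% of participants as the target. For the secondary satisfaction item, section 4.3 says "feasibility will be inferred additionally, if the questionnaire item assessing overall satisfaction with tDCS and training equipment is rated by a participant" favourably in 60% of participants, and section 6.2 says this outcome "will be analyzed similarly to the primary outcome".

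**The concern.** Sections 1.5 and 6.1 both say when feasibility is to be inferred, for the same criterion, and each gives its own count. They cannot be read as a target and a test of that target, because 6.1 treats 18 as sufficient and 1.5 treats 23 as necessary. Nothing in the SAP ranks them.

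This is the trial's only primary outcome. If the result falls between the two counts, the analyst can report feasible or not feasible and cite the SAP for either.

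There is a second mismatch inside section 1.5 once the interval in 6.1 is applied: at exactly 23 of 30, the count in 1.5 is met but its confidence-limit condition is not.

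**Working it through.** **Inputs.** N = 30, the 60% lower-limit condition and n = 23 (section 1.5); n = 18 and the Agresti-Coull method (section 6.1). Two-sided 95% level, z = 1.96. The SAP gives no expected success rate, so the true rates below are illustrative.

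**Step 1: reproduce n = 23.** The Wald lower limit is p − 1.96·√(p(1−p)/30).
- 22/30: 0.733 − 0.158 = 0.575
- 23/30: 0.767 − 0.151 = 0.615

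So 23 is the smallest count that clears 60% with a Wald interval. The figure in 1.5 is not an arithmetic slip.

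**Step 2: apply the interval named in 6.1.** Agresti-Coull uses ñ = n + z² = 33.84, p̃ = (x + z²/2)/ñ = (x + 1.92)/33.84, and limits p̃ ± 1.96·√(p̃(1−p̃)/ñ).

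| x of 30 | p̃ | half-width | 95% CI |
|---|---|---|---|
| 18 | 0.589 | 0.166 | 42.3% to 75.4% |
| 22 | 0.707 | 0.153 | 55.3% to 86.0% |
| 23 | 0.736 | 0.148 | 58.8% to 88.5% |
| 24 | 0.766 | 0.143 | 62.3% to 90.9% |

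Under the SAP's own method the smallest qualifying count is 24 (80%). At 23/30 the Wilson (59.1%), Jeffreys (59.6%) and Clopper-Pearson (57.7%) lower limits also fall short of 60%.

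**Step 3: can the rules be reconciled?** No. At 18/30 the lower limit is 42.3% (Agresti-Coull) or 42.5% (Wald), far below 60%. The disputed outcomes are 18 to 22 on the stated counts, and 18 to 23 if the condition in 1.5 is read with Agresti-Coull.

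**Step 4: how often would this matter?** Exact binomial, X ~ Bin(30, p). The chance of opposite answers is P(X≥18) − P(X≥23), or P(X≥18) − P(X≥24) with the Agresti-Coull count.

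| True rate | P(X≥18) | P(X≥23) | P(X≥24) | 18 vs 23 disagree | 18 vs 24 disagree |
|---|---|---|---|---|---|
| 50% | 0.181 | 0.003 | 0.001 | 18% | 18% |
| 55% | 0.359 | 0.012 | 0.004 | 35% | 36% |
| 60% | 0.578 | 0.044 | 0.017 | 53% | 56% |
| 65% | 0.780 | 0.124 | 0.059 | 66% | 72% |
| 70% | 0.916 | 0.281 | 0.160 | 63% | 76% |
| 75% | 0.978 | 0.514 | 0.348 | 46% | 63% |
| 80% | 0.997 | 0.761 | 0.607 | 24% | 39% |
| 90% | 1.000 | 0.992 | 0.974 | under 1% | 3% |

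Below the target, the 18-of-30 rule declares feasibility with probability 18% at a true 50% and 36% at 55%. The 24-of-30 rule does so with 0.1% and 0.4%.

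**The case against.** The best defence is that the SAP has in effect already chosen. Section 6.1 is the operative analysis section. It calls the analysis descriptive, gives the observed-60% rule and puts no threshold on the interval. Section 4.2 agrees and 1.2 reads most naturally the same way, so the confidence-limit sentence in 1.5 may be a leftover from planning. That is a fair reason for the sponsor to prefer the observed-60% rule. It does not remove the conflict, because 1.5 is worded as a condition for inferring feasibility and says how many participants must meet it.

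It is also fair that the 23-versus-24 point is secondary. Section 1.5 names no interval method, 23 is correct for Wald, and only one outcome is affected, and then only if the confidence-limit rule is kept. But this is a pass/fail cut-off, and Agresti-Coull is the only method the SAP names.

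Two further cautions stand in part:
- **Denominator.** All counts assume 30 participants, and the SAP does not name the analysis set for the primary outcome. The Agresti-Coull cut-off is 23 at N = 29 and 22 at N = 28. The criterion should therefore be the rule, with the count as its value at the planned N.
- **Satisfaction item.** Sections 4.3 and 6.2 do not contradict each other. The case for aligning them rests on 6.2 saying that the item is handled like the primary outcome.

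**Conclusion.** The concern holds and needs correcting before the data are seen. The SAP contains two decision rules for its primary outcome that give opposite answers for 18 to 22 successes of 30, and for 23 as well when the condition in 1.5 is evaluated with the interval in 6.1. On the stated counts the chance of landing in the disputed range is between 24% and 66% for true rates from 60% to 80%. It fades to under 1% at 90%. These probabilities rest on a denominator of 30, independent participants with a common success rate, and assumed true rates. The contradiction itself rests on none of them. The target in section 1.2 is compatible with either rule.

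**What to change.** Before the data are seen, state one rule, its interval method and the matching count, in the same words in sections 1.5, 4.2 and 6.1.

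- **Option A**, better supported if feasibility is to be inferred with error control: feasibility is inferred if the lower limit of the two-sided 95% Agresti-Coull interval is at least 60%. Replace n = 18 in 6.1 and the plain 60% in 4.2, and change 76% and n = 23 in 1.5 to 80% and n = 24 of 30.
- **Option B**: keep 18 of 30, delete the confidence-limit requirement and n = 23 from 1.5, and call 18 of 30 (interval 42.3% to 75.4%) a descriptive benchmark. Report that it would be met with probability 18% and 36% at true rates of 50% and 55%.

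Under either option, name the denominator and apply the chosen rule to the satisfaction criterion in 4.3 and 6.2.

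**Cost.** The edit is wording only. Option A has a price at N = 30 that should be disclosed: the chance of declaring feasibility is 1.7%, 16%, 35%, 61% and 85% at true rates of 60, 70, 75, 80 and 85%, against 4.4%, 28%, 51%, 76% and 93% with a cut-off of 23. Option B costs no sample size but gives up a confidence-based claim.

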6.3 Safety/Tolerability

Safety outcomes will be reported separately as incidences (n, incidence rate with 95%CI) in total and by intervention group based on the safety analysis set. Incidence rates and 95%CI will be based on poisson regression models that account for the different observation periods for each participant. Group comparisons will be done using incidence rate ratios and 95%CI. Results of safety analysis will be interpreted and discussed thoroughly also for minor group differences, since statistically significance is not of importance here.

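### Under the 18-of-30 rule in section 6.1, the pooled feasibility proportion does not protect a conclusion about active tDCS, and no estimate by arm is planned

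*SAP*

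**What the plan says.** - **What is claimed.** SAP 1.2 frames the hypothesis as the feasibility of "the self-application of tDCS combined with cognitive training by participants themselves" at home.
- **Who is counted.** Section 1.4: "Random allocation to experimental and control groups, respectively, will be performed with a 1:1 ratio". The control arm does the same six training sessions with sham stimulation. Section 1.5: "With 15 participants per stimulation group (anodal vs. sham stimulation), we will be able to scope the general feasibility of this home-based intervention".
- **The criterion.** Section 6.1: "Feasibility will be inferred when 60 % of the participants (n =18) complete at least two-thirds (n=4) of the home-based sessions successfully". Section 4.2 agrees: "Feasibility will inferred if 60% of the participants will have successfully performed two thirds (n= 4) of the planned sessions". Section 1.2 also sets 60% of all participants. Section 6.1 plans one point estimate with one Agresti-Coull 95% CI.
- **A competing rule.** Section 1.5 instead wants the lower 95% confidence limit at 60% and translates this into 23 participants.
- **Satisfaction.** The additional feasibility criterion in 4.3, analysed in 6.2, is likewise a single proportion over all participants.
- **What is split by arm.** Safety is reported "in total and by intervention group based on the safety analysis set" (6.3), and the baseline table in 6.5 has a column for each group. No section plans this for feasibility. The general sentence on descriptive statistics in section 6 does not mention arms.

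**The concern.** A session fails if it is not registered as complete, or if the participant makes contact about a problem or rescheduling. Handling the equipment is common to both arms, but reasons to stop or call need not be. Section 4.4 collects itching, pain, burning and fatigue, and 6.3 plans to compare safety outcomes between groups, so the plan itself allows that tolerability may differ. If it does, a good sham arm can lift the pooled proportion over the threshold while the active arm falls below it.

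At stake is how far the conclusion reaches. A later trial would deploy active stimulation. A reader of the primary result would see one proportion and one interval, and could not tell whether they describe the active arm.

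**Working it through.** **Inputs.** Section 1.5: "we chose a sample size of N = 30", 15 per group. Section 6.1: threshold 60%, two-thirds of six sessions, Agresti-Coull 95% CI. Section 1.5: competing threshold 23.

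**The plan's own figures.** 0.60 × 30 = 18 and 2/3 × 6 = 4; both reproduce. The 23 of section 1.5 reproduces with a Wald interval (lower limit 61.5%). With the Agresti-Coull formula named in 6.1 the lower limit at 23/30 is 58.8%, so 24/30 is needed (62.3%).

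**Fewest anodal successes that still pass.** With 15 per arm, sham contributes at most 15, so the minimum is T − 15 for a pooled threshold T.

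| Rule | T | Minimum anodal | Most anodal failures |
|---|---|---|---|
| 6.1, point estimate | 18 | 3/15 (20%) | 12/15 |
| 1.5, as stated | 23 | 8/15 (53%) | 7/15 |
| 1.5, with Agresti-Coull | 24 | 9/15 (60%) | 6/15 |

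**Agresti-Coull intervals for one arm.** With z = 1.96, let n′ = n + z² and p′ = (x + z²/2)/n′. The interval is p′ ± z√(p′(1 − p′)/n′). For n = 15, n′ = 18.84.

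- 5/15: p′ = (5 + 1.92)/18.84 = 0.367, half-width 0.218, CI 15.0% to 58.5%.
- 3/15: p′ = 0.261, half-width 0.198, CI 6.3% to 46.0%.
- 13/15: CI 60.9% to 97.5%.
- 9/15: p′ = 0.580, half-width 0.223, CI 35.7% to 80.2%.

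Under the 6.1 rule, 5/15 anodal plus 13/15 sham gives 18/30 and passes, although the upper confidence limit for the anodal arm is below 60%.

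**How likely this is.** The SAP gives no expected success rate by arm, so the rates below are assumptions. The columns are exact binomial probabilities with 15 per arm under the 18/30 rule.

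| Assumed true rate, anodal / sham | P(declare feasible) | P(declare and at least 8/15 anodal fail) |
|---|---|---|
| 60% / 60% | 57.8% | 3.2% |
| 70% / 70% | 91.6% | 2.2% |
| 80% / 80% | 99.7% | 0.3% |
| 40% / 80% | 58.4% | 37.9% |
| 40% / 90% | 81.7% | 60.4% |

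Under the 23/30 rule the last column is zero in every row, because at least 8/15 anodal participants must succeed.

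**The case against.** **Pooling fits the stated aim.** Sections 1.2 and 4.2 define feasibility over the participants as a whole, 1.5 speaks of general feasibility, and success is operational: cloud-registered completion and no participant-initiated contact. The trial is double-blind and both arms follow the same home procedure. This stands. Using all 30 participants to judge the procedure is a legitimate choice, and the point is not that pooling is an error.

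**The consequence needs a large arm difference.** With equal true rates of 60% to 80%, declaring feasibility while most of the active arm fails has a probability of at most 3.2%. The 5/15 and 13/15 split is a gap of 53 percentage points (87% − 33%, from unrounded values). This also stands; the splits are illustrative.

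**The stronger reading.** A reader might infer that this trial can declare tDCS feasible while a clear majority of those on active stimulation fail. The SAP does not support that without qualification, because the section 1.5 rule excludes it. Nor does a split of 9/15 anodal plus 15/15 sham at 24/30 show it: the anodal arm is then at 60%, so nothing is contradicted.

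**Some of the information appears elsewhere.** Tolerability is reported by group (6.3). The per-protocol set (2.1) consists of those who met the session criterion, so its group sizes would largely reveal the counts by arm. That is implied rather than promised, comes without an interval, and does not cover satisfaction.

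**A gate on the anodal arm would go too far.** Also requiring 9/15 in the anodal arm sets a second threshold on 15 people. At a true 70% in both arms it lowers the chance of passing from 91.6% to 83.5%. This stands, and the fix contains no such gate.

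**Conclusion.** The point holds in a limited form. Under the 60% point-estimate rule of 6.1, shared by 1.2 and 4.2, the pooled criterion can be met with as few as 3 of 15 anodal successes, and the plan contains no feasibility estimate by arm that would show it. Under the section 1.5 rule the minimum is 8 of 15, or 9 of 15 with Agresti-Coull, and the active arm cannot mostly fail. Because the SAP does not reconcile these rules, the size of the problem depends on which one is kept. Under either, a pooled result alone does not say how well active tDCS was tolerated as a home procedure.

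The minimum counts assume the planned 15/15 split; a small imbalance from stratified blocks would shift them slightly. The probabilities rest on assumed success rates. Nothing in the document indicates that the arms will differ; it only gives no basis for assuming that they will not.

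**What to change.** 1. Settle whether 18/30 or the confidence-limit rule of section 1.5 decides feasibility, since this determines how much the pooled result says about the active arm.
2. Keep the pooled proportion as the primary criterion.
3. In 6.1 and 6.2, also report the session and satisfaction criteria by stimulation group with Agresti-Coull 95% CIs, and the between-arm difference with its 95% CI, all descriptively.
4. State in advance that the pooled result supports feasibility of the home procedure, and that any statement about active tDCS will cite the anodal-arm estimate and CI. Set no separate anodal pass/fail threshold.

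The cost is a few sentences in the SAP and extra table columns, with no new data or participants. The arm-level intervals will be wide (about ±22 percentage points at 9/15), so they will describe the active arm only roughly.
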